After all interviews have been conducted, we will notify remaining invited participants that their participation is no longer needed.

Data Analysis and Power.

Data Analysis. In order to evaluate the pilot study, we will examine (a) recruitment and retention rates and (b) satisfaction surveys (i.e., accessible, usable, convenient, relevant, and helpful) and (c) rates of alcohol initiation and escalation, negative consequences, abstainer prototype favorability, abstainer injunctive and descriptive norms, engagement in and enjoyment of alternative activities, and endorsement of personal goals that do not involve alcohol, which will provide base rates and variance in outcomes to determine adequate power for a future clinical trial R01 application.

Feasibility will be assessed by (1) the proportion of first-year college students ages 18-19 who meet inclusion criteria and enroll for the study and (2) the proportion of participants who complete the TM intervention, the 6-week post-intervention assessment and 3, 6, and 9-month follow-ups compared to assessment only control. The length of time to recruit our target enrollment will be assessed as an outcome of feasibility.

Acceptability will be assessed with responses from a brief satisfaction survey included in the 6-week post-intervention assessment. Acceptability will be determined by (1) the proportion of participants who find the intervention acceptable (e.g., acceptability of content delivery method), usable (e.g., ease of viewing and interacting with TM intervention content), relevant (e.g., relevance of material), and helpful (e.g., finding content helpful, beneficial, important), (2) participants' ratings of individual TMs, (3) whether participants shared the texts with anyone else, (4) the proportion of participants who would recommend the study, and (5) the proportion of participants who found the program to be favorable overall. Responses from the post-intervention interviews will also be used as a measure of acceptability.

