To explore treatment differences and to determine preliminary effect sizes in drinking outcomes, this pilot will have five repeated measures (i.e., baseline, 6-week post-intervention, 3, 6, and 9-month follow-ups), yielding up to 1500 Level 1 observations (repeated-measures) across 300 Level 2 cases (people). Prior to inferential statistics, univariate and bivariate descriptive statistics will be used to assess distributions and simple associations among variables. Primary outcomes are alcohol initiation (binary outcome) and escalation in terms of number of drinks and consequences (both count outcomes). Additional outcomes are abstainer prototype favorability, abstainer injunctive and descriptive norms, engagement in and enjoyment of alternative activities, and endorsement of personal goals that do not involve alcohol, which are modeled as normally distributed outcomes. Given the repeated measures design, generalized linear mixed models (GLMM; Raudenbush & Bryk, 2002) will be used. GLMM (aka hierarchical generalized linear models) allow for non-normal outcomes and missing data. The model below represents the basic analytic model for a count outcome:

$$\text{Level 1: } \log(E[DV_{ti}]) = \pi_{0i} + \pi_{1i}(6\text{-week})_{ti} + \pi_{2i}(3\text{-month})_{ti} + \pi_{3i}(6\text{-month})_{ti} + \pi_{4i}(9\text{-month})_{ti} \quad (1)$$

$$\begin{aligned} \text{Level 2: } \pi_{0i} &= \beta_{00} + \beta_{01}(Tx)_i + r_{00i} & \pi_{3i} &= \beta_{30} + \beta_{31}(Tx)_i + r_{30i} \\ \pi_{1i} &= \beta_{10} + \beta_{11}(Tx)_i + r_{10i} & \pi_{4i} &= \beta_{40} + \beta_{41}(Tx)_i + r_{40i} \\ \pi_{2i} &= \beta_{20} + \beta_{21}(Tx)_i + r_{20i} \end{aligned}$$

where t indexes time point and i indexes participants. DV_{ti} represents the outcome for each individual at each time point. Time will be coded with *four* dummy variables (6-week $_{ti}$, 3-month $_{ti}$, 6-month $_{ti}$, and 9-month $_{ti}$) that compare follow-up assessments to baseline (reference category). Tx is a dummy coded variable comparing the TM intervention condition to the AOC condition. We will test sex and age in all analyses. We will determine preliminary effect sizes using the

model shown in equation 1. The four treatment by time interactions (β_{11} to β_{41}) compare the change in the outcome since baseline between intervention and control.

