Through collaboration with the Associate Director of Residence Life at UNT, [name], we will be sharing study information with the UNT first-year students residing in their halls. We will share general information about what the study is about and what participation will look like with students. We will also be passing out currently approved flyers and handouts to students with our contact information so students are able to reach out to us with any questions they may have. Residence Life will not have access to information about participants enrolled in the study.

G. Risk/Benefit Assessment

- 1) Describe the *level of risk*, and if more than minimal, describe how this research holds the prospect of a *direct benefit for the subjects*. If there is NO direct benefit to subjects, state such in protocol and in the consent documents.

There is potential risk for participating in The Freshman Experience Project. The risks associated with participation are primarily related to the sensitivity of some of the questions. Participants will be asked about thoughts, feelings, and personal difficulties that may be private, as well as behaviors such as alcohol use and drug use. These questions may make participants feel uncomfortable or may seem intrusive, or participants may become concerned about their drinking or other health behaviors as they answer the questions. In addition, participants are asked to report on illegal behaviors, such as drinking under the legal age, or using controlled substances. Participants are free to skip over any questions they do not wish to answer. There is also risk for confidentiality; we discuss procedures below to protect participant confidentiality.

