We have taken steps to protect participants against potential risks posed by their participation in this research. Participants will be fully informed of the range of items and the most sensitive and personal items in the consent form, and will be informed that they are free not to answer any question they wish not to answer, and can refuse to participate or withdraw from participation at any time without penalty. Participants will still be able to submit a survey with unanswered questions and will still receive full compensation when submitting a survey with unanswered questions. Psychological risks of experienced invasion of privacy or increased awareness or concern about one's behavior as a result of completing the assessments and interview and potential loss of confidentiality will be addressed as a risk in the consent documents. All data and other information in the proposed research will be maintained confidentially, but will not be anonymous due to the longitudinal nature of participation. In order to protect against risks posed by a potential loss of confidentiality, we will take the following steps: First, all data will be identified only by a unique PIN, which will be randomly generated for study purposes. PINs will be embedded in individual survey links such that PINs do not need to be entered by participants or known by participants. Identifiable information entered online (such as contact information)

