**REFINING AND PILOTING A TEXT MESSAGING INTERVENTION TO DELAY
ALCOHOL INITIATION AND REDUCE ALCOHOL USE ESCALATION AMONG
ABSTAINER AND LIGHTER DRINKER COLLEGE STUDENTS**

**NCT03750838
11/16/2023**

Analytic Plan

To assess feasibility of the intervention, we examined targeted recruitment, enrollment, and retention rates. To feasibility, we examined response rates for text message intervention rating for those assigned to the intervention condition. For acceptability, we assessed overall ratings of acceptability as well as mean ratings of content area-specific text messages. Rates of alcohol initiation (yes/no) were examined at each time point as were means and standard deviations of the number of drinks per week at each time point.

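### The SAP's raw per-wave drinking rates and means describe only those who answered, and it does not carry forward the protocol's mixed model that allows for missing data

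*Protocol*

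**What the plan says.** The SAP is one paragraph, headed Analytic Plan. On feasibility it says "we examined targeted recruitment, enrollment, and retention rates". On drinking it says "Rates of alcohol initiation (yes/no) were examined at each time point", and it treats the mean and SD of weekly drinks in the same way. It states no analysis set, denominator, arm split or missing-data rule, and it does not mention a mixed model.

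The protocol goes further in its Data Analysis and Power text:

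- Feasibility includes the proportion completing the intervention and each named assessment: "the 6-week post-intervention assessment and 3, 6, and 9-month follow-ups compared to assessment only control". What makes a survey complete is not defined.
- The drinking outcomes are to supply the base rates and variances for powering a later R01 trial.
- A generalized linear mixed model (GLMM) over five waves is specified. Such models are said to "allow for non-normal outcomes and missing data". No missingness assumption or sensitivity analysis is stated.

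On answering items, section G.1 says "Participants are free to skip over any questions they do not wish to answer". Section G.4 adds: "Participants will still be able to submit a survey with unanswered questions and will still receive full compensation". The drinking items are not excepted.

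**The concern.** A raw mean at a wave averages over the people who answered the drinking items at that wave. It estimates the mean for all randomised students only if non-response at that wave is unrelated to drinking. The protocol itself gives reasons for caution. Its risk section notes that participants are asked to report illegal behaviour, including underage drinking, and that the data are confidential but not anonymous. Students whose drinking has risen could plausibly drop out, or could submit with those items blank.

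What is at stake is the pilot's main quantitative product. If the mean and SD come from a selected subset, the error passes into the next trial's sample size. The next trial also needs to know what share of each arm yields a usable drinking outcome, and a count of submitted surveys does not by itself give that.

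**Working it through.** **The plan's own figure.** 300 participants × 5 waves = 1,500 observations, which matches the protocol's stated maximum. The protocol words it as an upper limit, and it is reached only if every outcome is present at every wave. Allocation is 150 per arm.

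**What the documents do not give.** There is no drop-out rate, item non-response rate or expected initiation rate. Every input below is an assumption.

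**1. Mean drinks.** Simulate two waves of skewed, zero-inflated weekly drinks with within-person correlation 0.6. Make 5% to 30% missing at the second wave, with log-odds of missing rising 0.3 to 1.0 per SD of earlier drinking.

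- The raw second-wave mean is about 2% to 22% below the true mean.
- Runs with other outcome generators gave 1% to 13% low at 5–10% missing, and 5% to 24% low at 20–30% missing.
- An estimate that uses the earlier wave removes essentially all of this bias. It does so because missingness was made to depend on that wave.
- If the sign of the dependence is reversed, so that lighter drinkers are missing, the raw mean is too high.

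**2. Initiation at the first follow-up.** Every baseline abstainer reports zero earlier drinks, so under this mechanism all have the same chance of being missing and there is no selection among them. In simulation, initiation among earlier-wave abstainers was 0.237 true against 0.236–0.237 observed. If missingness instead follows an unobserved propensity to drink, the worst case was 0.225.

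**3. Cumulative initiation at later waves.** Here someone already known to have initiated can be missing, and a raw per-wave rate drops that person. Let *u* be the share with data and *RR* the rate in the missing relative to the observed:

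observed = true / [*u* + (1 − *u*)·*RR*]

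- True 30%, *u* = 0.90, *RR* = 2: 0.30 / 1.10 = 27.3%.
- True 30%, *u* = 0.80, *RR* = 2: 0.30 / 1.20 = 25.0%.
- Check of the second: 0.80 × 25% + 0.20 × 50% = 30%. The missing tenth of all participants who had initiated can be restored to the extent that their initiation was reported at an earlier wave.
- If the first line were control and the second the text-message arm, a 2.3-point gap (27.3 − 25.0) would appear with no true difference.

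Starting instead from an observed 30% with *u* = 0.80:

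| Rate in the missing | Implied true rate |
|---|---|
| Half the observed | 0.80 × 30% + 0.20 × 15% = 27% |
| Same | 30% |
| Twice the observed | 0.80 × 30% + 0.20 × 60% = 36% |
| None / all initiated | 24% / 44% |

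**4. Usable surveys.** Usable share = submitted × (1 − blank share).

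- 90% submitted, 0% blank: 90.0% (270 of 300).
- 90% submitted, 5% blank: 85.5% (256 of 300).
- 80% submitted, 10% blank: 72.0% (216 of 300).

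**The case against.** Several stronger readings are tempting, and the documents do not support them.

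- *Retention is a single pooled figure.* The protocol names each assessment and compares with control. The SAP speaks of rates in the plural and does not say that they are pooled. It is silent, which is a different matter.
- *Retention is overstated.* That requires surveys with blank drinking items to occur and to be counted as complete. Neither is shown, and with no blanks the gap is zero.
- *The payment rule is a flaw.* It protects participants' freedom not to answer. The gap lies in how outcomes are summarised.
- *Initiation is biased as much as drinks.* Step 2 shows that it is not at the first follow-up.
- *The mixed model was chosen because of drop-out.* The protocol's stated reason is the repeated-measures design, and tolerance of missing data is given as a property of the model.

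There is also real mitigation. The protocol allows up to 8 emails, 8 texts and 3 calls per assessment, with payments rising from $20 to $40, and a Certificate of Confidentiality is to be obtained. Follow-ups ask when drinking began and reassess lifetime use, so a missed wave can be recovered if the student returns. Missingness may therefore be at the low end of the range. Recovery helps initiation only if the analysis uses it, however, and the SAP does not say that it does.

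Descriptive summaries are reasonable in a pilot, and the SAP does not withdraw the mixed model. But the protocol ties that model to effect sizes and does not say that the base rates will come from it. On either reading, nothing in the SAP protects the base rates from selective non-response.

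**Conclusion.** The point holds in a limited form. As written, the SAP's drinking summaries describe responders at each wave, and the model that would use earlier answers is not carried forward, although these figures are meant to power another trial. Under the assumed 5% to 30% missing, dependence of 0.3 to 1.0 log-odds per SD and correlation 0.6, raw mean drinks are about 2% to 22% low, with the sign reversed if lighter drinkers are missing. First-wave initiation among baseline abstainers is unaffected by that mechanism. Later cumulative initiation can be affected in either direction, by an amount the documents do not allow one to fix. This is worth correcting, but it does not show that any reported figure is wrong.

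**What to change.** In the SAP:

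1. Estimate mean drinks and initiation by arm and wave from the protocol's GLMM, averaged over the random effects so that the results are population means and rates. Multiple imputation using each person's earlier waves would also serve.
2. Carry forward initiation that a participant has already reported.
3. Show the raw figures beside these estimates, with a missing-data sensitivity range in both directions, such as the table above. The model corrects only for missingness explained by the answers it uses.
4. Report by arm and wave the number of surveys submitted and the number with the initiation item and the Daily Drinking Questionnaire answered. Use the second as the denominator of the raw figures.

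Leave the right to skip items with full payment unchanged. The SAP is written in the past tense, so the additions should be dated and labelled as such.

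The cost is modest extra analysis on data the surveys already collect. The usable-data retention figure may be slightly lower than the submitted one.

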**REFINING AND PILOTING A TEXT MESSAGING INTERVENTION TO DELAY
ALCOHOL INITIATION AND REDUCE ALCOHOL USE ESCALATION AMONG
ABSTAINER AND LIGHTER DRINKER COLLEGE STUDENTS**

**NCT03750838
11/16/2023**

Analytic Plan

To assess feasibility of the intervention, we examined targeted recruitment, enrollment, and retention rates. To feasibility, we examined response rates for text message intervention rating for those assigned to the intervention condition. For acceptability, we assessed overall ratings of acceptability as well as mean ratings of content area-specific text messages. Rates of alcohol initiation (yes/no) were examined at each time point as were means and standard deviations of the number of drinks per week at each time point.

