and gave permission to be contacted for future research opportunities. We will not contact any participants who did not give permission to be contacted for future research opportunities. These interviews will provide further feedback on the feasibility and acceptability of this intervention. Newly enrolled first-year college students will be randomized to the TM intervention or assessment only control. We hypothesize the TM Intervention will be feasible and acceptable to abstainer and lighter drinking students, including being accessible, usable, convenient, relevant and helpful. We further hypothesize that receiving the TM intervention will be associated with less initiation and escalation of drinking, fewer negative consequences, more favorable prototypes of abstainers and lighter drinkers, greater perceived abstaining and light drinking norms, greater engagement and enjoyment of alternative activities, and greater endorsement of personal goals that do not involve alcohol at the 6-week post-intervention assessment and 3, 6, and 9-month follow-ups relative to assessment only control.

B. Background and Significance - *Briefly* sketch the background leading to the present proposal. Describe the contributions that the study may make to the health of human beings and/or to the scientific community, using documentation from the literature, where appropriate. Although it is helpful for the Board to have a decent understanding of the basis for conducting a research project, it is *not* necessary to have a full-blown literature review or extensive background and rationale for the proposed research plan of activity.

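### For drinking outcomes the SAP names no text-message-versus-control contrast or effect measure and omits consequences, a protocol primary outcome, while neither citing nor withdrawing the protocol's model

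*SAP*

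**What the plan says.** **Protocol, Data Analysis and Power.** The outcomes are set out as follows: "Primary outcomes are alcohol initiation (binary outcome) and escalation in terms of number of drinks and consequences (both count outcomes". Time enters as four dummy variables that "compare follow-up assessments to baseline (reference category". A treatment dummy sets the text-message (TM) arm against assessment-only control, and the four treatment-by-time terms "compare the change in the outcome since baseline between intervention and control". On the effect sizes it says "We will determine preliminary effect sizes using the" model in equation 1, which is presented as the basic form for a count outcome.

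The same section lists what the pilot will examine, including "rates of alcohol initiation and escalation, negative consequences, abstainer prototype favorability, abstainer injunctive and descriptive norms", to supply base rates and variability for planning a later trial.

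**Protocol, Specific Aims.** Aim 3 includes preliminary effect sizes. Its hypotheses are stated "at the 6-week post-intervention assessment and 3, 6, and 9-month follow-ups relative to assessment only control".

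**SAP, Analytic Plan.** This is a single paragraph. For feasibility, "we examined targeted recruitment, enrollment, and retention rates". For drinking, the complete text is the sentence beginning "Rates of alcohol initiation (yes/no) were examined at each time point as were means and standard deviations of the number of drinks per week". The only mention of an arm concerns response rates to the message ratings within the intervention condition.

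**The concern.** The protocol treats the pilot's drinking analysis as comparative: it explores treatment differences and takes effect sizes from a model with a control arm. The SAP, dated later, describes only summaries by time point. Someone following the SAP alone would produce no stated TM-versus-control effect and no result at all for consequences. Someone reading both documents cannot tell whether the model and the third primary outcome were kept, replaced or left out, or why.

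Time-point summaries without an arm comparison would be hard to interpret here. The protocol's background expects drinking to rise on entry to college. Its benefit section says that completing the surveys may itself lower drinking. Its measures section uses different recall periods at different assessments. A same-time comparison with control deals with all three; a trend over time does not.

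**Working it through.** **1. The plan's own figures.** 300 people × 5 assessments = 1,500 observations, and 300 / 2 = 150 per arm. Both agree with the protocol. Neither document states an alpha, a power target or a target effect, so there is no power calculation to reproduce.

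**2. The two documents side by side.**

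| Item | Protocol | SAP |
|---|---|---|
| Initiation | primary, binary | rates at each time point |
| Number of drinks | primary, count | weekly means and SDs at each time point |
| Consequences | primary, count; questionnaire named in the measures section | not mentioned |
| Arm contrast | four treatment-by-time terms | none named |
| Effect measure | from equation 1 | none named |
| Additional outcomes | four domains | not mentioned |

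The SAP therefore names 2 of 3 primary outcomes. Of the four additional domains (prototypes, norms, alternative activities, personal goals), the measures section collects personal goals at baseline only. At most 4 − 1 = 3 domains can have follow-up results. A word search of the SAP paragraph finds no occurrence of consequence, control, group, difference, model, effect or confidence.

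**3. What the SAP's summaries can deliver.** There are two readings.

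- *By arm:* crude differences follow for initiation and drinks. Nothing follows for consequences.
- *Pooled:* nothing follows about the arm difference. With equal arms and illustrative values, (150 × 3 + 150 × 3) / 300 = 3.0 and (150 × 2 + 150 × 4) / 300 = 3.0, so one pooled mean fits a ratio of 1.0 or of 0.5.

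The SAP does not say which reading applies.

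**4. The denominator for initiation.** The inclusion criteria admit current light drinkers, who cannot newly initiate. Suppose a share q has already initiated at baseline and the later risks among the rest are p1 and p0. The cumulative full-sample rates are then q + (1 − q)p, and their difference is (1 − q)(p1 − p0). With assumed q = 50%, p1 = 20% and p0 = 40%, the full-sample rates are 0.5 + 0.5 × 0.2 = 60% and 0.5 + 0.5 × 0.4 = 70%. The difference is 10 points, against 20 points among those at risk. The SAP states no denominator.

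**5. Rough precision at one follow-up.** Retention and rates below are assumptions, since the documents give none.

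- Standardised mean difference, half-width 1.96 × √(2/n): n = 150 gives 0.226 SD; n = 120 (80% retention) gives 0.253 SD.
- Risk difference, half-width 1.96 × √(2p(1 − p)/n), with p from 20% to 50%: n = 150 gives 9.1 to 11.3 points; n = 120 gives 10.1 to 12.7 points; n = 75 (half the arm at risk, full retention) gives 12.8 to 16.0 points.

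These show that contrasts can be estimated but will be imprecise. They do not predict the model's own standard errors.

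**The case against.** The best reply is that silence is not withdrawal. The SAP nowhere says that it replaces the protocol's analysis section, which still gives outcomes, distributions, time coding and contrasts. This is also a pilot: the protocol speaks of exploring and of preliminary estimates, and descriptive summaries meet its base-rate purpose for initiation and drinks. All of that stands, and it limits the point to an incomplete plan with no cross-reference. It does not answer the absence of a primary outcome or of the effect sizes that the protocol made an aim.

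Several stronger readings are tempting, and the documents do not support them.

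- *The model was dropped, or dropped after the results were seen.* The SAP's past tense indicates that it was written after the analyses, but says nothing about what was decided or when. The protocol's future tense, 129 days earlier, does not show that the model was still pending. The same document speaks of recruitment in summer 2021 and a launch in fall 2020 as still to come.
- *No effect size can be obtained.* That would require the summaries to be pooled, which the SAP does not say.
- *A baseline-referenced model cannot be fitted for initiation.* It is not estimable among baseline non-initiators, whose baseline values are all zero, but the protocol states no such restriction. Logistic fits to simulated full samples of 150 per arm, with assumed baseline initiation of 30%, 50% and 70%, converged. These were marginal models, not the mixed model itself.
- *The protocol's model is not identified.* Five random effects plus a residual variance give 15 + 1 = 16 covariance parameters against 15 variances and covariances for a normal outcome. But equation 1 is given for a count, and the protocol does not clearly commit the normal outcomes to the same random effects.

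**Conclusion.** The point holds as an unexplained gap between protocol and SAP, and it should be closed before the SAP is relied on. The SAP omits one of three primary outcomes and names no TM-versus-control contrast or effect measure for the other two. The missing contrast is one omission, and multiplying it across outcomes and visits would not make it larger. The conclusion rests on the wording alone. It needs no assumption about retention, event rates or whether the summaries are pooled. Those assumptions affect only the illustrations and the expected width of the intervals.

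**What to change.** 1. Report initiation, drinks and consequences by arm at each time point.
2. For drinks and consequences, report the protocol's treatment-by-time contrasts (2 outcomes × 4 follow-ups = 8) with 95% intervals, labelled exploratory. Simplify the random effects if the model does not fit, and say so.
3. For initiation, compare arms at the follow-ups among participants who had not initiated at baseline, and give that denominator by arm. The reason is the at-risk group.
4. Report by arm the additional outcomes that were measured at follow-up, or state that they were not analysed. Reconcile the baseline-only collection of personal goals with the Aim 3 hypothesis about them at follow-up.
5. Do not present new wording as prespecified. Label each outcome or analysis dropped or replaced as a deviation from the protocol, with the reason and its timing relative to data access.

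The cost is some extra analysis of data that the protocol already plans to collect, and wide intervals that must be presented as exploratory.
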